7.2 COMPLETE CASE ANALYSIS

If there is more than 10% missing data then complete analysis will be used as a sensitivity analysis. For a complete case analysis, if a patient has missing data for any factor within the model then this patient will be removed from the analysis.

7.3 RANDOM SURVIVAL FORESTS MISSING DATA

As part of the sensitivity analyses random survival forests will be produced, described in Section 8.1.1.2 Random Survival Forests, which will use the R package ‘randomForestSRC’. For our predictive model, a call to rfsrc() will be made, and in the presence of missing data the option ‘n.action = “na.impute”’ will be used to impute missing data. The missing data algorithm which will be envoked can be summarized as (6):

- Variables with missing data are imputed by randomly drawing from the in-bag non-missing data. Split statistics can be calculated from the imputed data so that cases are assigned to daughter nodes.
- Following the node split, imputed data is set back to missing.
- Repeat the first two steps until the terminal node is reached. Missing data within the terminal nodes are imputed using in-bag, non-missing terminal node data.
- Records where all outcome and variable information is missing are removed. Variables which have only missing values are removed.

7.4 PCS MISSING DATA

No imputation will be used for missing PCS data.

7.5 CSQ MISSING DATA

No imputation will be used for missing CSQ data. In the event of missing data the corresponding domain score will not be calculated.

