6.1.1.2.1 PCS – Pain Catastrophising Scale

The Pain Catastrophising Scale (PCS) is a 13 item questionnaire around thoughts and emotions experienced during pain, with each question on a 5 point scale (0 = 'Not at all' to 4 = 'All the time'). There are three subscales of PCS: Rumination (thinking deeply), exaggeration and helplessness. [Table 2](#) shows an overview of the items which belong to each domain.

Table 2 Overview of Domains for PCS ([5](#))

Domain	Items
Rumination	8, 9, 10, 11
Exaggeration	6, 7, 13
Helplessness	1, 2, 3, 4, 5, 12

Total scores and domain scores are derived by summing the scores of the individual items. The highest possible score of PCS is 52, and a total score of ≥ 20 indicates a clinically relevant level of catastrophisation. PCS will be considered both in terms of individual domain scores and total scores. PCS total score will be analysed as a continuous variable as well as a dichotomous variable (<20 vs ≥ 20).

For the handling of missing data when deriving PCS scores, see Section [7.4](#).

PCS is collected at all visits (Inclusion visit, V1, V2, V3, V4, V5, V6 and any additional visits in the case of discontinuation of Tofacitinib).

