6.1.1.2.2 CSQ – Coping Strategies Questionnaire

The Coping Strategies Questionnaire (CSQ) evaluates cognitive coping and, in its French version, is split into 5 domains: “Distraction”, “Catastrophising”, “Distancing from Pain”, “Ignoring Pain Sensations” and “Praying”. The CSQ consists of 21 items in total and for each item, subjects rate the frequency of their use of each coping strategy on a 4-point Likert-type scale. CSQ is collected on the CRF as the following: 1: Never, 2: Sometimes, 3: Often and 4: Very often. In order to consider values comparable to the standard CSQ French Version, the following mapping will be done.

CSQ Text Value	CRF Value	Map to standard value
Never	1	0
Sometimes	2	1
Often	3	2
Very Often	4	3

This endpoint is considered in terms of the 5 domains, and a total score is not considered for CSQ. Domain scores are derived by summing the individual items scores that make-up the domain. Details of the 5 domains are provided below.

Domain	Items as numbered on CRF	Domain Score Range
Distraction	2, 10, 11, 19, 20	0 – 15
Catastrophising	3, 9, 15, 18	0 -12
Distancing from Pain	1, 5, 13, 21	0 – 12
Ignoring Pain Sensations	6, 7, 8, 14, 16	0 – 15
Praying	4, 12, 17	0 - 9

CSQ is collected at all visits (Inclusion visit, V1, V2, V3, V4, V5, V6 and any additional visits in the case of discontinuation of Tofacitinib).

For the handling of missing CSQ data, see Section [7.5](#).

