7.8 FACIT-FATIGUE QUESTIONNAIRE MISSING DATA

If any items are not answered the following approach will be taken:

If more than 50% of the items are non-missing, a prorated subscale will be derived as

$$\text{Prorated Subscale Score} = \frac{\text{Sum of individual answered items} * 13}{\text{Number of answered questions}}$$

If 50% or more of the items are missing the score will be set to missing.

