8.2.9 Summary of Analyses

Table 8 Summary of Main Analyses

Outcome	Analysis Set	Supports Protocol Objective Number	Subgroups	Statistical Method	Covariates/ Strata	Missing Data
Time to discontinuation of Tofacitinib	Full Analysis Set (FAS)	1	None	Cox PH model	Univariate model selection, followed by backwards selection on the variables in Figure 2 .	Missing data indicators
Sensitivity Analysis – Only to be used in the event of >10% missing data: Time to discontinuation of Tofacitinib	FAS	1 – Sensitivity Analysis	None	Cox PH model	Univariate model selection, followed by backwards selection on the variables in Figure 2 .	Complete Case Analysis
Sensitivity Analysis: Time to discontinuation of Tofacitinib	FAS	1 – Sensitivity Analysis	None	Random Survival Forests	Variables in Figure 2 , following methods seen in Section 8.1.1.2 Random Survival Forests .	Random Survival Forests missing data algorithm.
Sensitivity Analysis: Time to discontinuation of Tofacitinib	Month 3 Analysis Set	1 – Sensitivity Analysis	None	Cox PH model	Univariate model selection, followed by backwards selection on the variables in Figure 2 and Das28-4 CRP at Baseline.	Missing data indicators
Sensitivity Analysis: Time to discontinuation of Tofacitinib	Month 3 Analysis Set	1 – Sensitivity Analysis	None	Random Survival Forests	Variables in Figure 2 and DAS28-4 CRP at Month 3, following the methods seen in Section 8.1.1.2 Random Survival Forests .	Random Survival Forests missing data algorithm.
Time to discontinuation of Tofacitinib	FAS	2	None	Cox PH model	Baseline CSQ and baseline PCS	No missing data methods used.
Time to discontinuation of Tofacitinib	FAS	2	None	Cox PH model	Last recorded CSQ and PCS before discontinuation.	No missing data methods used.
Time to discontinuation of Tofacitinib	FAS	2	None	Cox PH model	Change from baseline to last recorded CSQ and PCS before discontinuation.	No missing data methods used.

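### The baseline behavioural Cox model may drop any patient with one blank among 34 PCS and CSQ items, and the SAP does not say how a partly completed PCS is scored

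*SAP*

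**What the plan says.** **PCS.** SAP 6.1.1.2.1 says that the PCS "is a 13 item questionnaire around thoughts and emotions experienced during pain", and that "Total scores and domain scores are derived by summing the scores of the individual items". On blanks, SAP 7.4 says only: "No imputation will be used for missing PCS data".

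**CSQ.** SAP 6.1.1.2.2: "The CSQ consists of 21 items in total", and "Domain scores are derived by summing the individual items scores that make-up the domain". The domains have 5, 4, 4, 5 and 3 items, so every item feeds a domain. SAP 7.5 adds: "In the event of missing data the corresponding domain score will not be calculated".

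**Models.** The protocol summary calls the behavioural analysis the key secondary one. SAP 8.1.1.1 fits three Cox models, each with the PCS total and the five CSQ domains entered jointly. They use baseline values, the last evaluation before discontinuation (or the last visit), and change from baseline. For all three, Table 8 in SAP 8.2.9 has "No missing data methods used", and SAP 8.2.6 agrees. SAP 7 sets out the missing-indicator method for the primary analysis and specified sensitivity analyses only.

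**Other instruments.** FACIT-Fatigue also has 13 items. For it SAP 7.8 says "If more than 50% of the items are non-missing, a prorated subscale will be derived as" the sum of the answered items scaled up to 13. SAP 7.6 fills a missing EQ-5D dimension with the mean of the others. SAP 7.7 follows the producer's rules for the SF-12.

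**The concern.** The strictest item-level handling falls on the two instruments behind the first secondary objective, and no reason is given. One unanswered item removes a CSQ domain, and a patient without that domain drops out of a model that needs all six scores. This costs events. It also biases the hazard ratios if patients who skip items differ in pain, fatigue or risk of stopping. No sensitivity analysis is planned for these models.

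The PCS has a separate gap. SAP 7.5 states what follows from a blank and SAP 7.4 does not. One programmer could set the total to missing; another could add up the answered items, which scores the blank as 0. The second route loses no PCS total but lowers it by up to 4 points per blank, and could move a patient below the 20-point cut used in SAP 6.1.1.2.1 and 8.1.3. The two outcomes are alternatives: any one dataset suffers one or the other.

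**Working it through.** **Plan's own figures (Protocol 9.5).** 50 candidate factors × 0.3 = 15 variables; 15 × 10 = 150 events; 150 / 0.50 = 300 patients. These reproduce. SAP 2.1 still says 500 patients; the percentage losses below do not depend on which is used.

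**Inputs.** PCS 4 + 3 + 6 = 13 items; CSQ 5 + 4 + 4 + 5 + 3 = 21; total 34. The item skip rate q is an assumption, because the documents give none; I use 0.5%, 1% and 2%.

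**Baseline model, PCS voided by a blank.**
- Independent skips: share kept = (1 − q)^34.
- Clustered skips: beta-binomial with within-patient correlation ρ from 0.05 to 0.30. Share kept = B(a, b + 34) / B(a, b), where a = q(1 − ρ)/ρ and b = (1 − q)(1 − ρ)/ρ.
- Events kept = 150 × share, taking skipping as unrelated to discontinuation. Events per variable = events / 6. Confidence-interval width grows by 1/√share.

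| q | Kept, independent | Patients of 300 | Events of 150 | Events per variable | CI width | Lost, independent | Lost, clustered |
|---|---|---|---|---|---|---|---|
| 0.5% | 0.843 | 253 | 126.5 | 21.1 | × 1.09 | 16% | 3–9% |
| 1% | 0.711 | 213 | 106.6 | 17.8 | × 1.19 | 29% | 7–18% |
| 2% | 0.503 | 151 | 75.5 | 12.6 | × 1.41 | 50% | 13–33% |

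With independent skips, events per variable reach 10 (60 events) at q = 1 − (60/150)^(1/34) ≈ 2.7%.

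**Baseline model, blank PCS item summed as zero.** Only the 21 CSQ items can exclude a patient: 0.99^21 = 0.81 kept at 1%.

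**Change model at q = 1%, independent skips, PCS voided.** Share kept = 0.711 × P(usable follow-up form).
- Only the last form counts: 0.99^68 = 0.505, about 51%.
- Last scorable of two forms: 0.711 × (1 − 0.289²) = 0.65.
- Last scorable of three forms: 0.711 × (1 − 0.289³) = 0.69.

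SAP 8.2.6 limits these analyses to assessments before permanent discontinuation. Early stoppers therefore have fewer forms to fall back on.

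**Correlations and logistic models at q = 1%.** The loss is per score. PCS total: 1 − 0.99^13 = 12%. CSQ domains: 1 − 0.99^3 = 3% to 1 − 0.99^5 = 5%. Comparing two time points needs the score at both.

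**With the SAP 7.8 rule applied to the PCS total and each CSQ domain (independent skips).** The chance that any of the six baseline scores is missing is 0.04%, 0.15% and 0.6% at q = 0.5%, 1% and 2%.

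**The case against.** The best reply is that the size rests wholly on an assumed skip rate, and that independence is the pessimistic end. That stands: clustering cuts the 1% loss from 29% to 7–18%, so the figures are scenarios and not a forecast. Patients hand the forms back to the physician (Protocol 9.1.4), electronic completion is allowed (9.6.3) and research assistants chase omissions (9.10.1). All of this may lower q, though none of it guarantees complete items, and paper remains a described route.

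Four stronger readings are tempting and not supported:
- That the change model must lose about half its patients at 1%. The plan uses the last evaluation available, which may mean the last scorable form; then about 65–69% are kept with two or three follow-up forms.
- That one blank removes a patient from the correlations and logistic models as well. SAP 8.1.3 fits the scores in separate univariate models, and the correlations are score by score.
- That a PCS blank certainly voids the total. This is the natural reading of a plain sum with no imputation, and scoring a blank as zero is arguably an imputation, but SAP 7.4 does not say so.
- That the baseline model becomes unstable. It stays above the plan's benchmark of 10 events per variable over the range shown, and SAP 4 sets no formal hypotheses.

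It is also fair that a FACIT-Fatigue rule does not by itself validate proration for the PCS or the French CSQ. That argues for keeping the strict scores as a sensitivity run, and not for leaving the rule as it is.

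**Conclusion.** The concern holds as a conditional one. If a blank voids the PCS total, as it does a CSQ domain, the baseline behavioural model needs 34 answered items and nothing else in the plan rescues an incomplete patient. At an assumed 1% skip rate the loss is about 29% of patients with independent skips and about 7–18% with clustered skips. The corresponding losses are 16% and 3–9% at 0.5%, and 50% and 13–33% at 2%. The main cost is precision, with bias added if skipping relates to pain, fatigue or stopping.

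The change model is more exposed. If only the last form counts, its events per variable fall to 6.3 at 2% with independent skips (150 × 0.98^68 = 38 events, over 6 covariates). The wording gap in SAP 7.4 needs closing at any skip rate, because two programmers could derive different PCS totals from the same text. The 150 events and 300 patients are planned figures before any exclusions from the Full Analysis Set.

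**What to change.** Amend the SAP as follows.
- **7.4:** state that a blank PCS item is never summed as zero.
- **7.4 and 7.5:** apply the 7.8 rule. Prorate the PCS total, each PCS subscale and each CSQ domain when more than 50% of its items are answered; otherwise set the score to missing.
- **8.1.1.1 and 8.2.6.1:** use these scores in the three behavioural Cox models and the other behavioural analyses, and repeat with strict complete-item scores as a sensitivity run.
- **8.1.1.1:** state that the last evaluation available is the last scorable one.
- **Table 8:** update the missing-data entries to match.

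The cost is a few sentences and a change to the scoring program, with no new data. The downside is small: proration assumes that a skipped item resembles the answered ones. That is weakest for the 3-item Praying domain, where two answers would stand in for the third.

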7.6 EQ-5D-3L MISSING DATA

Missing weighted dimension scores are replaced by the mean of the non-missing weighted dimension scores. If a weighted score is missing and replaced in this way by a mean weighted score of zero, step 3 of the algorithm described in Section 6.1.1.2.14 is applied.

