6.1.1.2.14 EuroQoL EQ-5D-3L

The European Quality of Life (Euro-QoL) developed the EQ-5D-3L questionnaire. It is a standardised, self-reported instrument used to evaluate health-related quality of life. It is copyrighted and consists of 5 domains of questions:

1. Mobility
2. Self-care
3. Usual activities
4. Pain/discomfort
5. Anxiety/depression

Each question domain has 3 levels, of which a patient will choose the most appropriate level for each, see [Table 4](#).

Table 4 EQ-5D-3L Scores

Dimension	Response	Score
Mobility	I have no problems in walking about	1
	I have some problems in walking about	2
	I am confined to bed	3
Self-care	I have no problems with self-care	1
	I have some problems washing or dressing myself	2
	I am unable to wash or dress myself	3
Usual activities (e.g. work, study, housework, family or leisure activities)	I have no problems with performing my usual activities	1
	I have some problems with performing my usual activities	2
	I am unable to perform my usual activities	3
Pain/discomfort	I have no pain or discomfort	1
	I have moderate pain or discomfort	2

	I have extreme pain or discomfort	3
Anxiety/depression	I am not anxious or depressed	1
	I am moderately anxious or depressed	2
	I am extremely anxious or depressed	3

The score for each dimension is weighted in accordance with [Table 5](#).

Table 5 EQ-5D-3L Weightings (10)

EQ-5D Dimension	Score = 1	Score = 2	Score = 3
Mobility	0	0.155	0.372
Self-Care	0	0.212	0.326
Usual Activities	0	0.156	0.189
Pain/Discomfort	0	0.112	0.265
Anxiety/Depression	0	0.090	0.204

The following algorithm is then applied to calculate the EQ-5D Total Score:

1. If all five EQ-5D dimensions have a score of 1 then the EQ-5D Total Score is 1.
2. If any of the five EQ-5D dimensions have a score of 3, then the EQ-5D Total Score is:

$$1 - \left(\sum_1^s \text{weighted dimension score} \right) - 0.174$$

3. If none of the five EQ-5D dimensions has a score of 3, then the EQ-5D Total Score is:

$$1 - \left(\sum_1^s \text{weighted dimension score} \right)$$

For the handling of missing weighted dimension scores, see Section [7.6](#).

The Euro QoL EQ-5D-3L Questionnaire is completed at all visits (Inclusion visit, V1, V2, V3, V4, V5, V6 and any additional visits in the case of discontinuation of Tofacitinib).

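### The EQ-5D-3L missing-dimension rule can impute a weight above the dimension's own maximum, give totals below the scale minimum, and score a partly blank questionnaire as full health (minor)

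*SAP*

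**What the plan says.** SAP 6.1.1.2.14 scores the EQ-5D-3L in three steps. Each dimension's level (1, 2 or 3) is converted to a weight in Table 5, and the weights are specific to the dimension, for example "Mobility 0 0.155 0.372" against "Usual Activities 0 0.156 0.189". A patient at level 1 throughout scores 1. The further deduction of 0.174 depends on a level-3 answer: "If any of the five EQ-5D dimensions have a score of 3, then the EQ-5D Total Score is" 1 minus the sum of the weights minus 0.174. With no level 3, the total is 1 minus the sum of the weights.

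SAP 7.6 deals with blanks: "Missing weighted dimension scores are replaced by the mean of the non-missing weighted dimension scores". One special case follows: "If a weighted score is missing and replaced in this way by a mean weighted score of zero, step 3 of the algorithm" applies. Nothing limits the number of blanks, and nothing checks the imputed weight against the range of the dimension that it stands for.

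Other instruments have their own rules. PCS has no imputation (7.4). For CSQ, "In the event of missing data the corresponding domain score will not be calculated" (7.5). SF-12v2 follows its producer's rules (7.7). FACIT-Fatigue is prorated when more than half of the items are answered (7.8).

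**The concern.** Replacing a blank by the mean of the answered items is defensible when all items share one scale, as the 13 FACIT-Fatigue items do (0 to 4 each). The EQ-5D-3L weights do not. Level 3 costs 0.372 on mobility but only 0.189 on usual activities, so averaging across dimensions can give a loss that the missing dimension cannot produce. The 0.174 term adds a second problem: a blank that was really a level 3 leaves no trace unless another dimension was also answered 3. A mean of zero is carried through as no loss at all.

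At stake are the by-visit summaries and changes from baseline of a protocol secondary endpoint (SAP 8.2.6.2), its correlations with PCS and CSQ over the 24 timepoint pairings in Figure 3 (8.2.6.1), and one of the 23 candidate characteristics in the logistic model for baseline PCS (8.2.6.5). The questionnaires are completed by patients on paper or ePRO (Protocol 9.4 and 9.6.3), so skipped items are plausible.

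**Working it through.** **Inputs** (SAP 6.1.1.2.14, Table 5; weights for levels 1 / 2 / 3):

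- mobility 0 / 0.155 / 0.372
- self-care 0 / 0.212 / 0.326
- usual activities 0 / 0.156 / 0.189
- pain/discomfort 0 / 0.112 / 0.265
- anxiety/depression 0 / 0.090 / 0.204

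**Assumption.** The 0.174 is deducted only when an answered dimension is at level 3. Apart from the zero-mean case, 7.6 does not say how the term works with blanks.

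**Scale from complete data.** The SAP prints no minimum. From its own algorithm, the worst state is 1 - (0.372 + 0.326 + 0.189 + 0.265 + 0.204) - 0.174 = 1 - 1.356 - 0.174 = -0.530. The best is 1. The next best is 1 - 0.090 = 0.910.

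**One dimension missing, the other four at level 3.** Imputed weight = (sum of the four observed weights) / 4. Total = 1 - observed sum - imputed weight - 0.174.

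| Missing | Observed sum | Imputed weight | Own maximum | Total |
|---|---|---|---|---|
| Usual activities | 1.167 | 0.29175 | 0.189 | -0.633 |
| Anxiety/depression | 1.152 | 0.288 | 0.204 | -0.614 |
| Pain/discomfort | 1.091 | 0.27275 | 0.265 | -0.538 |
| Self-care | 1.030 | 0.2575 | 0.326 | -0.462 |
| Mobility | 0.984 | 0.246 | 0.372 | -0.404 |

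The first three lie below -0.530.

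**All one-missing patterns.** There are 5 x 3^4 = 405.

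- The imputed weight exceeds the missing dimension's maximum in 37: 20 with usual activities missing (observed sum above 4 x 0.189 = 0.756), 16 with anxiety/depression missing (above 4 x 0.204 = 0.816) and 1 with pain missing (above 4 x 0.265 = 1.060). In each of the 37, the total is below every value that the patient could truly have.
- The total is below -0.530 in 4: the first three rows above, and anxiety/depression missing with usual activities at level 2 and the rest at level 3, which gives -0.573.

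**More than one missing.** Totals below -0.530 arise in 7 of 270 patterns with two missing (lowest -0.779), 6 of 90 with three (lowest -0.919) and 2 of 15 with four. The extreme has only mobility answered, at level 3: 1 - 5 x 0.372 - 0.174 = -1.034.

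**Every answered dimension at level 1.** The mean is 0, step 3 applies, and the total is 1.000. If the one missing dimension were truly at level 3, the total would be 1 - weight - 0.174: mobility 0.454, self-care 0.500, pain 0.561, anxiety 0.622, usual activities 0.637. At level 2 it would be at most 0.910. With one dimension answered at level 1 and four blank, the rule still gives 1.000. If the four blanks were all level 3, the true total would lie between -0.158 and -0.341, depending on which dimension was answered.

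**Size and direction of error.** Taking all 243 complete states and blanking each dimension in turn gives 243 x 5 = 1,215 cases. Error (imputed minus true) runs from -0.292 (usual activities truly level 1, the rest level 3) to +0.546 (mobility truly level 3, the rest level 1). It exceeds 0.1 in absolute value in 53%: about 25% upward and 28% downward. The mean error is +0.011. In the 160 cases whose true state has no level 3, the mean is 0.000 (range -0.159 to +0.212).

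**The case against.** The strongest reply is that the defect is real but rarely matters. Totals below the minimum need extreme answers: all 4 one-missing patterns have both mobility and self-care at level 3, and -1.034 needs four of five dimensions blank. The false 1.000 does harm only if the blank hides a problem, and the zero-mean clause shows that the authors considered that case. EQ-5D-3L is one of many secondary endpoints, by default only summarised (SAP 2.4), one of 11 endpoints in the correlations, and one of 23 candidates in an exploratory model. The SAP states no formal hypotheses (section 4). All of this stands and limits the severity.

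Three stronger readings are tempting, and the documents support none of them.

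- *The rule biases utilities systematically.* Under equal weighting the errors go both ways and average +0.011. They are specific to the answer pattern: upward when mild answers surround a severe blank, downward in the reverse case.
- *More than half of imputed scores are off by over 0.1.* The 53% counts 243 states equally and treats the hidden answer as unrelated to the others. It is not a patient distribution.
- *The SAP contradicts itself because PCS and CSQ are not imputed.* SAP 8.2.6 provides for rules specific to each endpoint, and 7.7 and 7.8 also allow scores to be completed. Different rules are not a contradiction.

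What the reply does not meet is that the rule can return values that the instrument cannot produce, and a score of full health from a single answered question. Stating the zero-mean case in advance does not make its result right.

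**Conclusion.** SAP 7.6 is wrong as written, and the matter is minor. Averaging across unequal weights, with no limit on blanks, gives an impossible imputed weight in 37 of 405 one-missing patterns and a total below -0.530 in 4 of 405. It gives 1.000 whenever all answered dimensions are at level 1. These results use only the SAP's weights and algorithm, plus the stated assumption about the 0.174 term.

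The counts are of possible answer patterns, not of patients. The documents give no item-missing rate and no distribution of states, so the effect on any mean, correlation or odds ratio cannot be estimated. A reader might infer that the primary Cox model is affected. That cannot be checked, because the figure listing its candidate factors is not available in the text.

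**What to change.** Replace the text of SAP 7.6 with: *If any EQ-5D-3L dimension is missing, the Total Score is set to missing for that visit.* Tabulate the observed level of each dimension alongside, so that partial answers are still reported. Every total then lies between -0.530 and 1. The CSQ domains already work this way.

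The cost is one sentence in the SAP and the loss of a few partly completed questionnaires from the index summary. Dropping them is itself an assumption, since skipping an item may be related to severity, so the number of totals lost at each visit should be reported.

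Two lighter repairs are weaker. A cap on the number of blanks leaves every one-missing result above unchanged. Truncating totals at -0.530 alters only 4 of the 37 patterns with an impossible weight and leaves the other 33. Neither removes the 1.000 given when one dimension is blank and the other four are at level 1.
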